**Table 15.2.1 5: Full Analysis Set- Patient satisfaction with Spiolto® Respimat®**

Patient satisfaction		N	%
visit_satisfaction_spiolto	Very satisfied		
Patient overall satisfaction with Spiolto® Respimat® treatment	Satisfied		
	Rather satisfied		
	Neither satisfied nor dissatisfied		
	Rather dissatisfied		
	Dissatisfied		
	Very dissatisfied		
	Not answered		
	Missing		
	Total		
visit_satisfaction_inhalator	Very satisfied		
Patient satisfaction with inhaling from the Respimat® device	Satisfied		
	Rather satisfied		

Patient satisfaction		N	%
	Neither satisfied nor dissatisfied		
	Rather dissatisfied		
	Dissatisfied		
	Very dissatisfied		
	Not answered		
	Missing		
	Total		
visit.satisfaction_handling	Very satisfied		
Patient satisfaction with handling of the Respimat® inhalation device	Satisfied		
	Rather satisfied		
	Neither satisfied nor dissatisfied		
	Rather dissatisfied		
	Dissatisfied		
	Very dissatisfied		
	Not answered		
	Missing		
	Total		

**Table 15.2.1 6: Full Analysis Set- Patient's willingness to continue Spiolto® Respimat®**

visit.spiolto_continued	N	%
Willing to continue treatment		
Yes		
No		
Missing		
Number of patients with visit 2		

**Table 15.2.1 7: Full Analysis Set- Reason for discontinuation of Spiolto® Respimat®**

visit.spiolto_spiolto_reason	N	%
Reason for treatment discontinuation		
Adverse event		
Serious adverse event		
Patient's wish		
Withdrawal of informed consent		
Lost to follow-up		
Patient's death		
Other		
Missing		
Number of patients with visit 2		

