9.7 DATA ANALYSIS

Planned analyses

More details will be described in the statistical analysis plan (SAP).

No formal hypothesis testing will be performed since this is a self-controlled study.

All patients who have received at least one dose of Spiolto[®] Respimat[®] will be included in the analysis; this is the treated set. All analyses will be performed on the treated set (as-treated analysis). If patients have missing values for an outcome, those patients will be excluded for that outcome's analysis. For example, if a patient is missing the CCQ score at Visit 1 and/ or Visit 2, that patient will be excluded from the analyses for the primary endpoint of therapeutic success and the secondary endpoint of change in CCQs from Visit 1 to Visit 2.

The assessment will be carried out using SAS[®] software. The statistical characteristics presented in the end-of-text tables will be N / mean / SD / min / median / max for continuous

variables. Tabulations of relative and absolute frequencies will be presented for categorical variables. Incidence rates and 95% CI will be given when appropriate.

The analyses will relate to the following data:

- Patient demographics (gender, age, height, weight)
- Comorbidities (main diagnosis and concurrent diagnosis according to MedDRA, version valid as at the time of database closure)
- COPD related and other concomitant medication (according to the WHO classification, version valid at the time of database closure)
- History of smoking
- Reported exacerbations
- Breathlessness based on mMRC score at visit 1
- Therapeutic success based on CCQ score; primary outcome
- Changes from Visit1 to Visit 2 in the CCQ and CCQ-4 score; secondary outcome
- Patient satisfaction with Spiolto[®] Respimat[®] at visit 2 only; secondary outcome
- General condition of the patient: evaluated by the physician (Physician's Global Evaluation (PGE)), secondary outcome
- Willingness to continue; secondary outcome
- Adverse Drug Reactions (ADR & SADR), fatal AEs, pregnancies
- GOLD spirometric classifications (1, 2, 3, 4) and GOLD patient groups (B, C, D)
- Details of treatment with inhaled respiratory agents before the study
- Details of treatment with respiratory agents during the study
- Reasons for ending treatment during the observation period
- Details of treatment continuation / discontinuation

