All pregnancy monitoring forms associated with Spiolto [®] Respimat [®]	7 calendar days

All serious ADRs and all fatal AEs must be documented in the eCRF and reported to the Pharmacovigilance department of Boehringer Ingelheim **within 24 hours** after getting knowledge of the event. The Boehringer Ingelheim NIS AE form must be printed from the eCRF and sent per fax.

Non-serious ADRs and pregnancies must be documented in the eCRF and reported to the Pharmacovigilance department of Boehringer Ingelheim **within 7 calendar days** after getting knowledge of the event. The Boehringer Ingelheim NIS AE form must be printed from the eCRF and sent per fax.

If there is no eCRF access at the time of the report, the NIS AE form must alternatively be filled out by hand and sent to the following address by fax within 24 hours / 7 days after becoming known:

Boehringer Ingelheim Pharma GmbH & Co. KG
Pharmacovigilance Germany (PV Germany)
[name]
[contact]
[contact] – [name]

In this case, these data must be entered into the eCRF as soon as possible when electronically available.

The same timelines apply if follow-up information becomes available for the respective events. In specific occasions the Investigator could inform the Sponsor upfront via telephone. This does not replace the requirement to complete and fax the NIS AE form.

Information required

For each reportable adverse event, the investigator should provide the information requested on the appropriate eCRF pages.

Reporting of related Adverse Events associated with any other BI drug

The investigator is encouraged to report all adverse events related to any BI drug other than the Spiolto[®] Respimat[®] according to the local regulatory requirements for spontaneous AE reporting at the investigator's discretion by using the locally established routes and AE report forms. The term AE includes drug exposure during pregnancy, and, regardless of whether an AE occurred or not, any abuse, off-label use, misuse, medication error, occupational exposure, lack of effect, and unexpected benefit.

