### 2.2 Display templates for in- or end-of-text reports

#### 2.2.1 End-of-text table templates

##### 2.2.1.1 15.1 Trial subject

##### 2.2.1.1.1 15.1.1 Disposition of subjects

Table 15.1.1 1: Disposition

	N (%)
Patients recruited {patient.id}	xx (100.0)
Patients with visit 1 {anamnesis.done}	xx (yy.y)
Reason for not performing Visit 1 {anamnesis.done_reason}	
Adverse event	xx (yy.y)
Serious adverse event	xx (yy.y)
Patient's wish	xx (yy.y)
Withdrawn consent	xx (yy.y)
Lost to follow-up	xx (yy.y)
Patient died	xx (yy.y)
Other	xx (yy.y)
Study participation not possible {patient.no_participation}	xx (yy.y)
Patients with visit 1, but no registration {anamnesis.done}{registration.registered_by}	xx (yy.y)
Patients not treated	xx (yy.y)
Patients included in Treated Set	xx (yy.y)
Patients with Visit 2 {visit.done}	xx (yy.y)
Reason for not performing Visit 2 {visit.done_reason}	
Adverse event	xx (yy.y)
Serious adverse event	xx (yy.y)
Patient's wish	xx (yy.y)
Withdrawn consent	xx (yy.y)
Lost to follow-up	xx (yy.y)
Patient died	xx (yy.y)
Other	xx (yy.y)
Patients with Visit 2- Continuation of medication after end of observation (Spiolto ® Respimat ® ) {visit.spolto_continued}	xx (yy.y)
Patients with Visit 2- Discontinuation of medication after end of observation (Spiolto ® Respimat ® )	xx (yy.y)
Reason for discontinuation of Spiolto ® Respimat ® {visit.spolto_reason}	
Adverse event	xx (yy.y)
Serious adverse event	xx (yy.y)
Patient's wish	xx (yy.y)
Withdrawn consent	xx (yy.y)
Lost to follow-up	xx (yy.y)
Patient died	xx (yy.y)
Other	xx (yy.y)

Patients included in FAS	xx (yy.y)
Reason for not included in FAS	
Available total CCQ score at visit 1 only	xx (yy.y)
Available total CCQ score at visit 2 only	xx (yy.y)
No available total CCQ score at all	xx (yy.y)
Not included in TS	xx (yy.y)

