**Table 15.1.4 32: Treated Set- Reason for therapy with Spiolto® Respimat® carried out irregularly**

visit.spioalto_regular_reason	N	%
Reason for irregular treatment		
Adverse event		
Serious adverse event		
Patient's wish		
Other		
Missing		
Number of patients with irregular treatment		

**Table 15.1.4 33: Treated Set- Changes of treatment with other COPD related therapies besides Spiolto® Respimat® since visit 1 [i.e. new therapy introduced or existing baseline therapy discontinued\*]**

visit.further_resp	N	%
Changes of treatment with other COPD related therapies		
No		
Yes		
Missing		
Number of patients in Treated Set with visit 2		

\*New therapy: New therapy in addition to already existing baseline therapies besides Spiolto® Respimat®

**Table 15.1.4 34: Treated Set- Changes of treatment with other COPD related therapies besides Spiolto® Respimat® since visit 1- Affected respiratory therapeutics (multiple answers possible)**

visit_resp.therapeutic		N	%
Changes of treatment with other COPD related therapies- Affected therapeutics			
New therapy in addition to already existing baseline therapies besides Spiolto® Respimat® introduced after visit 1	Short-acting β 2 -Agonist		
	Long-acting β 2 -Agonist		
	Short-acting anticholinergic		
	Long-acting anticholinergic		
	Long-acting anticholinergic and long-acting β 2 -Agonist in a fixed combination		
	Short-acting anticholinergic and short-acting β 2 -Agonist in a fixed combination		
	Long-acting β 2 -Agonist and inhaled corticosteroid in a fixed combination		
	Inhaled corticosteroid		
	Systemic corticosteroid		

visit_resp.therapeutic		N	%
Changes of treatment with other COPD related therapies- Affected therapeutics			
	Theophylline		
	Roflumilast (Daxas®)		
	Other		
	Number of patients in Treated Set with visit 2		
Components of existing baseline therapy at visit 1 discontinued since then	Short-acting $\beta_2$ -Agonist		
	Long-acting $\beta_2$ -Agonist		
	Short-acting anticholinergic		
	Long-acting anticholinergic		
	Long-acting anticholinergic and long-acting $\beta_2$ -Agonist in a fixed combination		
	Short-acting anticholinergic and short-acting $\beta_2$ -Agonist in a fixed combination		
	Long-acting $\beta_2$ -Agonist and inhaled corticosteroid in a fixed combination		
	Inhaled corticosteroid		
	Systemic corticosteroid		
	Theophylline		
	Roflumilast (Daxas®)		
	Other		
	Number of patients in Treated Set with visit 2		

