**Appendix 7: Other reasons for irregular treatment with Spiolto® Respimat® (free text)**

visit.spioolto_regular_reason_spc	N	%
Other reason for irregular treatment with Spiolto® Respimat®		
Reason 1		
Reason 2		
...		
Total		

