**Appendix 8: Other reasons for no continuation of Spiolto® Respimat® treatment (free text)**

visit.spioolto_reason_spec	N	%
Other reason for no continuation of Spiolto® Respimat® treatment		
Reason 1		
Reason 2		
...		
Total		

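### No coded reason for stopping Spiolto or using it irregularly covers insufficient effect, so the planned tables are likely to understate stopping for lack of effect

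*SAP*

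**What the plan says.** Protocol 9.7 lists among its analyses "Reasons for ending treatment during the observation period" but names no categories. The visit flow chart in Protocol 9.2.3 collects the rationale for discontinuation at Visit 2. Willingness to continue is a secondary outcome, used as a proxy for adherence (Protocol 9.3.2.2).

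The SAP supplies the categories:

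- Table 15.2.1 7 (Full Analysis Set, FAS), "Reason for treatment discontinuation": the seven options adverse event, serious adverse event, patient's wish, withdrawal of consent, lost to follow-up, death and other, plus a row for missing.
- Table 15.1.1 1 (disposition), block "Reason for discontinuation of Spiolto": the same seven options.
- Table 15.1.4 32, "Reason for irregular treatment": adverse event, serious adverse event, patient's wish and other, plus missing.

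Free text behind other is tabulated with N and % per reason, in Appendix 8 for not continuing and Appendix 7 for irregular use. The SAP has no free-text table for patient's wish.

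**The concern.** In an effectiveness study, the drug not helping is an obvious reason to stop it or to take it irregularly. The coded lists separate safety reasons from everything else, but give insufficient effect no place of its own. A physician whose patient stops because nothing improved must choose a less specific box. Patient's wish and other both fit.

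At stake is the reading of the tables that explain why patients did not continue. Stops for lack of effect filed as patient's wish look neutral. Those filed as other appear only as separate free-text wordings in an appendix. A reader of Table 15.2.1 7 would see counts for adverse events and none for insufficient effect, and could take the second to be rare when it was simply not asked.

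**Working it through.** No calculation settles this point. The planned sample size in Protocol 9.5 (1170 evaluable, and 1170/0.9 = 1300 enrolled) reproduces but does not bear on it. The check is to follow a stop for lack of effect through every place where it could be recorded.

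1. **Coded reason for stopping** (Table 15.1.1 1 discontinuation block; Table 15.2.1 7). There is no matching option. Both tables concern patients with a Visit 2, and the second also requires a total CCQ score at both visits, because that defines the FAS. Loss to follow-up and death should therefore be nearly empty here. In practice adverse event, serious adverse event, patient's wish and other carry most of the counts, with withdrawn consent as a further non-specific option.
2. **Coded reason for irregular use** (Table 15.1.4 32). There is no matching option.
3. **Free text under other** (Appendices 7 and 8). Lack of effect can be written here and would appear with N and %. The templates list reasons one by one and give no rule for grouping different wordings of the same reason.
4. **Patient's wish.** No free-text companion table exists for stopping or for irregular use. A case filed here cannot be recognised as lack of effect.
5. **Safety text.** Protocol 11.2 mentions "lack of effect, and unexpected benefit" only in the paragraph on the sponsor's other drugs. The AE form in Protocol Appendix 3 gives lack of effect as an example of other in its item on incorrect administration. SAP Table 15.3.2 14 tabulates that item as incorrect administration. Neither place records a reason for stopping Spiolto.

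Write L for the true number of stops for lack of effect, F for those written under other, and W for those filed as patient's wish or in any other coded box. Then L = F + W. The planned tables can show at most F, and only after someone groups the wordings. F equals L only if no site uses another box (W = 0), and nothing in the documents tells sites to avoid one.

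**The case against.** The strongest reply is that nothing is lost. Other carries free text, the SAP tabulates it, and a physician can write that the drug had no effect. This stands against any claim that the reason cannot be recorded or reported. It does not answer the undercount, because it covers only cases filed under other and comes without a grouping rule.

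Second, a reader might infer that treatment failure itself goes unreported. The documents do not support that. SAP Section 1 defines non-success as a CCQ decrease below 0.4, and Table 15.2.1 1 has a row for it. PGE and satisfaction are tabulated as well. Section 2.5 repeats success, CCQ change, PGE and satisfaction by continuation (no versus yes). Every patient in Table 15.2.1 7 has a known CCQ result. What is missing is the reason for stopping, which is a different quantity from the outcome.

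Third, a reader might infer that such stops inflate the adverse-event counts. That is conjecture, since no instruction sends lack of effect to that box. The safety tables on stopping use the action-taken field of the AE record, not the visit reason field.

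Fourth, it is tempting to extend the point to "Reason for not performing Visit 2", whose list also lacks the category. Missing a visit is not the same as stopping the drug, and a non-responder can still attend. Nor does the SAP contain a missing-data sensitivity analysis into which such patients could be fed: its two sensitivity analyses concern the visit interval and estimated exacerbation counts.

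Finally, Protocol 9.7 names no categories, so the SAP does not contradict it. That is right. The point is a weakness in the chosen lists, not an inconsistency between documents.

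**Conclusion.** The point holds in this limited form. No coded list for stopping Spiolto or for irregular use has insufficient effect. The reason is countable only from ungrouped free text under other, and the resulting count is a lower bound. That the tables will understate it assumes that at least some sites file such cases under patient's wish or another coded option. This is likely given the wording of the options, but the documents do not state it.

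The size cannot be given. The documents contain no rate of stopping Spiolto and no share of stops due to lack of effect. The 10% drop-out in Protocol 9.5 is a sample-size allowance, not a stopping rate. As pure assumption, 5% to 10% of 1300 stopping, with 30% to 50% of them for lack of effect, gives 1300 × 0.05 × 0.30 = 19.5 to 1300 × 0.10 × 0.50 = 65 patients. That range should not be read as an estimate of hidden cases: both rates are unsupported, and some of these patients would be visible in the free text.

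The primary analysis is unaffected. The consequence is confined to the description of why patients stopped or used the drug irregularly.

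**What to change.** Add insufficient effect as a coded option to visit.spiolto_reason and visit.spiolto_regular_reason. Add the matching row to the discontinuation block of Table 15.1.1 1 and to Tables 15.1.4 32 and 15.2.1 7.

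If the eCRF can no longer change, classify the free text of Appendices 7 and 8 into this category by a rule written into the SAP. Do this before database lock and without sight of the CCQ scores, and state beside the count that it is a lower bound because cases filed as patient's wish cannot be recovered.

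The cost is a small eCRF update and three table rows, or a short coding step.

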**2.2.1.1.5 15.3. Safety analysis**

Extent of exposure

**Table 15.3.1 1: Treated Set- Time between start of treatment and end of observation/discontinuation [weeks]**

anamnesis.spiocto_date; visit.date; visit.spiocto_last_date	N	Mean	Std	Min	Median	Max	Nmiss
Time between start of treatment and end of observation/discontinuation							

**Table 15.3.1 2: Treated Set- Survival status**

sae.therapy; visit.done_reason	N	%
Survival status		
Patient died		
Patient alive		
No. of patients in Treated Set		

Safety

**Table 15.3.2 1: Treated Set- Adverse events overall summary**

	N (%)
Number of patients	xx (100.0)
Patients with investigator defined drug-related AE {sae.spiocto_causality}	xx (yy.y)
Patients with investigator defined drug-related AE leading to discontinuation of trial drug {sae.spiocto_action_taken}	xx (yy.y)
Patients with serious AE {sae.sae}	xx (yy.y)
Fatal {sae.criteria_fatal}	xx (yy.y)
Life threatening {sae.criteria_life_theratening}	xx (yy.y)
Persistant or significant disability/incapacity {sae.criteria_disability}	xx (yy.y)
Hospitalization {sae.criteria_hospital}	xx (yy.y)
Prolongation of hospitalization necessary {sae.criteria_prolonged}	xx (yy.y)
Congenital anomaly/birth defect {sae.criteria_congenital}	xx (yy.y)
Other important medical event {sae.criteria_other}	xx (yy.y)
Patients with serious AE leading to discontinuation {sae.sae} {sae.spiocto_action_taken}	xx (yy.y)
Patients with serious drug-related AE {sae.sae} {sae.spiocto_causality}	xx (yy.y)

Drug-related adverse events (Drug-related AE)

**Table 15.3.2 2: Treated Set- Drug-related AE according to MedDRA-SOC and PT (event based)**

sae.nci		N	%
Drug-related AE (event based)			
SOC1	PT1		
	PT2		
	...		
SOC2	PT1		
	PT2		
	...		

sae.nci		N	%
Drug-related AE (event based)			
...	PT1		
	PT2		
	...		
Total			

**Table 15.3.2 3: Treated Set- Drug-related AE by MedDRA system organ class and preferred term- Maximum NCI grade per patient**

sae.nci		Grade 1		Grade 2		Grade 3		Grade 4		Grade 5		Total	
Drug-related AE-Maximum grade per patient		N	%	N	%	N	%	N	%	N	%	N	%
Any SOC													
SOC1	PT1												
	PT2												
	...												
SOC2	PT1												
	PT2												
	...												
...	PT1												
	PT2												
	...												
No. of patients in Treated Set													

**Table 15.3.2 4: Treated Set- Number of patients with drug-related AE occurring with share in preferred term greater than 5% by primary system organ class and preferred term**

	N (%)
Total with drug-related AE occurring with share in preferred term greater than 5%	xx (100.0)
Primary SOC {sae.nci}	xx (yy.y)
Preferred term	xx (yy.y)
...	xx (yy.y)

**Table 15.3.2 5: Treated Set- Drug-related AE- Worst outcome per patient**

sae.outcome	N	%
Drug-related AE- Worst outcome		
Recovered/Resolved		
Not yet recovered/resolved		
Recovered/resolved with sequelae		
Fatal		
Unknown		
No drug-related AE		
No. of patients in Treated Set		

Order: From best to worst: Recovered/resolved; Recovered/resolved with sequelae; Not recovered/Not resolved; Unknown; Fatal

**Table 15.3.2 6: Treated Set- Drug-related AE- Patients with at least one drug-related AE for which therapy was required**

sae.therapy	N	%
Drug-related AE- Therapy required		
No		
Yes		
Missing		
No drug-related AE		
No. of patients in Treated Set		

**Table 15.3.2 7: Treated Set- Drug-related AE- Patient pregnant at AE**

sae.pregnancy	N	%
Drug-related AE- Pregnant		
No		
Yes		
Not applicable		
Missing		
Total		

**Table 15.3.2 8: Treated Set- Drug-related AE- Week of pregnancy**

sae.pregnancy_week	N	Mean	SD	Min	Median	Max	Nmiss
Drug-related AE- Week of pregnancy							

**Table 15.3.2 9: Treated Set- Drug-related AE- Action taken concerning therapy (patient based; multiple answers possible)**

sae.nci; sae.spiocto_action_taken	N	%
Drug-related AE- Action taken		
Continued		
Reduced		
Stopped		
Increased		
Missing		
No. of patients with drug-related AE		

**Table 15.3.2 10: Treated Set- Drug-related AE leading to treatment discontinuation by MedDRA system organ class and preferred term**

sae.nci		N	%
Drug-related AE leading to discontinuation (patient based)			
Any SOC			
SOC1	PT1		
	PT2		
	...		
SOC2	PT1		
	PT2		

sae.nci		N	%
Drug-related AE leading to discontinuation (patient based)			
	...		
...	PT1		
	PT2		
	...		
No. of patients in Treated Set			

**Table 15.3.2 11: Treated Set- Drug-related AE- Improvement after stop of therapy (patient based; multiple answers possible)**

sae.spiocto_action_taken_stop		N	%
Drug-related AE- Improvement after stop			
No			
Yes			
Missing			
No. of patients with stop of treatment because of drug-related AE			

**Table 15.3.2 12: Treated Set- Drug-related AE- Re-exposition done for at least one event**

sae.spiocto_action_taken_expo		N	%
Drug-related AE- Re-exposition			
No			
Yes			
Not applicable			
Missing			
No. of patients with stop of treatment because of drug-related AE			

**Table 15.3.2 13: Treated Set- Drug-related AE- Recurrence of at least one TEAE after re-exposition**

sae.spiocto_action_taken_again		N	%
Drug-related AE- Recurrence after re-exposition			
No			
Yes			
Missing			
No. of patients with re-exposition			

**Table 15.3.2 14: Treated Set- Incorrect administration of medication (multiple answers possible)**

Incorrect administration of medication	N	%
sae.application_abuse		
Abuse/Incorrect use		
sae.application_medication_error		
Medication error		
sae.application_overdose		

Incorrect administration of medication	N	%
Overdosing		
sae.application_other		
Other		
Patients with incorrect administration		
Number of patients with drug-related AE		

Serious AE

**Table 15.3.2 15: Treated Set- Serious AE according to MedDRA-SOC and PT (event based)**

sae.nci; sae.sae		N	%
Serious AE (event based)			
SOC1	PT1		
	PT2		
	...		
SOC2	PT1		
	PT2		
	...		
...	PT1		
	PT2		
	...		
Total			

